7.0 Study Withdrawal/Discontinuation

Subjects can voluntarily withdraw from the study at any time by contacting any of the researchers on the study via any available means (personal contact, email, phone, etc.). If a researcher on the project wishes to withdraw a subject from the study, they will

contact the subject directly (personal contact, phone, email, etc.). Possible indications for withdrawal by a researcher include: concern that a subject could injure himself performing one of the exercise tasks in the study (perhaps due to poor coordination), results that do not meet the criteria for inclusion in the study, an abnormal response to exercise or hypoxic exposure, an abnormal response to Cetirizine, an inability to complete the exercise tests, inability of a subject to complete a task properly to obtain valid measures, etc.

8.0 Statistical Considerations

Paired t-tests will be used to determine differences between Cetirizine and Placebo trials for select dependent variables (e.g. mass, percent fat). A 2 x 2 (condition by time) repeated measures ANOVA will be used to determine pre- vs. post-test differences across conditions with select dependent variables (e.g. plasma histamine). A 2 x 5 (condition by time) repeated measures ANOVA with a priori simple main effects and a Bonferroni correction for multiple pairwise comparisons will be used to determine differences between conditions for select dependent variables (e.g. ventilation, VO_2 , SpO_2) obtained at each km of the 5km time trials.

A power analysis was completed using previous literature (Prefaut et al., *Med Sci Sports Exerc*, 1997). Their data examined the change in arterial PO_2 levels pre- and post-antihistamine, which relates to our outcome variable of arterial oxyhemoglobin saturation. From their data, we were able to calculate an interventional treatment effect (Cohen's d) of 0.61. Using a one tailed test to match our directional hypothesis, a power analysis with that treatment effect indicates that approximately 9 subjects will provide adequate statistical power (i.e. $1 - \beta > 0.80$) to show significant differences at the $p < 0.05$ level (experiment-wise error rate). With the potential for drop-outs and non-qualifiers after the initial $VO_{2\max}$ screening, we anticipate testing a total of 15 subjects.

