2.0 Rationale and Specific Aims

Specific Aim #1 – Determine the effect of Cetirizine (Zyrtec®) on exercise performance and arterial oxygenation with acute exposure to a simulated altitude

For this project, healthy subjects will perform steady state and progressive work rate exercise, endurance performance time trials, and repeated sprint performance time trials in the laboratory at a simulated altitude of 3000m (9900ft) after dosing with 10 mg of Cetirizine or a placebo in a repeated measures design. Non-invasive techniques (pulse oximetry, near-infrared spectroscopy [NIRS]) will be utilized to measure changes in arterial oxyhemoglobin saturation and skeletal muscle oxygenation at the level of the microvasculature during exercise.

It is expected that after Cetirizine, blood and muscle microvascular oxygenation during heavy exercise will improve compared to placebo, ultimately improving exercise performance at altitude.

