Study procedures: (Session 1) after completion of informed consent documents and questionnaires, height and weight will be measured. Body composition will be measured by bioelectrical impedance. Resting pulmonary function will then be performed as described by the American Thoracic Society (specific procedures and measurements are detailed under *“Resting Pulmonary Function Testing”* below). Following these measurements, subjects will be allowed to warm up on the cycle ergometer at a self-selected speed for 10 minutes. Subjects will then be fitted with a chest strap heart rate monitor and an oro-nasal face mask. A pulse oximeter sensor will also be placed on the subject's forehead to non-invasively measure arterial oxyhemoglobin saturation. Optodes from a near-infrared spectroscopy device will be placed on the subject's thigh and secured with a Velcro strap, in order to non-invasively measure oxygenated and deoxygenated heme-O₂ carriers in the skeletal muscle.

The maximal oxygen uptake test will begin with subjects pedaling at 50W, with subjects instructed to keep RPMs between 80 and 110. The workload will increase by 25W each minute until volitional exhaustion or until RPMs fall below 70 for more than five seconds. After completion of the maximal oxygen uptake test and following a 15-minute rest period, subjects will be asked to complete a familiarization 5km time trial on the cycle ergometer breathing a hypoxic inspirate (14.3% O₂, simulating 3000m) in as short of a time as possible (most subjects require between 8 and 12 minutes). Subjects will be able to self-select cadence and resistance on the ergometer.

(Session 2 and 3) Upon arrival at the lab, subject will be given either 10 mg of Cetirizine in pill form or a placebo (10 mg of gelatin in capsule form). Subjects will be allowed to sit comfortably or lie down for 60 minutes. Following this rest period, approximately 5 ml of blood will be drawn from an antecubital vein. Subjects will then be allowed to warm up

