on the cycle ergometer at a self-selected speed for 10 minutes. Following the warm-up, subjects will be fitted with a chest strap heart rate monitor, an oro-nasal face mask, a pulse oximeter sensor, and near-infrared spectroscopy optodes. Subjects will then be asked to complete two 5-minute cycling bouts at a constant, moderate intensity (as will be determined individually according to each subject's maximal oxygen uptake test performed on Session 1, details below). Subjects will be allowed 5 minutes of passive recovery after each of the 5-minute cycling bouts. Following the second recovery period, subjects will be asked to ride 5km, completing the distance in as short of a time as possible. Subjects will be allowed to shift gears on the bike at will and pedal at any RPM desired. Feedback on distance completed will be shown on a video monitor and verbally announced every 1km. During the TT, respiratory flow-volume measures will be completed by having the subjects complete two inspiratory capacity (IC) maneuvers near the end of each kilometer of the TT. Immediately following the TT, approximately 5 ml of blood will be drawn from an antecubital vein.

Demographic and screening variables: Age, height, weight, sex, body mass index, body composition (estimated percent lean body mass and fat mass), pulmonary function measures (total lung capacity, vital capacity, forced expiratory volume in one second, lung diffusing capacity, and maximal voluntary ventilation).

Dependent variables: exercise metabolic measures (VO₂, VCO₂, ventilation, heart rate), dyspnea and rating of perceived exertion during the 5km TT, time to completion of the 5km TT, power output during the 5km TT, muscle oxygenation, plasma histamine levels.

Specific Measures:

Height and weight: Height will be measured using a standard wall mounted, sliding height measuring board (stadiometer). Weight will be measured by an electronic scale.

Body composition: Subject stands in bare feet on an electrode imbedded scale (Tanita) and holds on to electrode imbedded handles. An unnoticeable electrical current is passed through the subject for 2 seconds, from which resistance to electrical flow is measured and body composition is estimated.

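### Does it matter that Section 8.0 illustrates the paired t-test with mass and percent fat and never names 5 km time-trial time?

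*Combined protocol and SAP*

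**What the plan says.** Section 8.0 lists three methods, each with examples introduced as illustrations. Paired t-tests are for "differences between Cetirizine and Placebo trials for select dependent variables (e.g. mass, percent fat"). A 2 x 2 repeated measures ANOVA is for pre/post variables, with plasma histamine as the example. A 2 x 5 repeated measures ANOVA is for variables recorded at each kilometre, with ventilation, VO2 and SpO2 as examples and a Bonferroni correction for its pairwise comparisons.

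Section 5.0 places the two paired-t examples in Session 1: "after completion of informed consent documents and questionnaires, height and weight will be measured. Body composition will be measured by bioelectrical impedance". It classes them apart from the outcomes: "Demographic and screening variables: Age, height, weight, sex, body mass index, body composition". The written steps for Sessions 2 and 3 open with dosing ("Upon arrival at the lab, subject will be given either 10 mg of Cetirizine in pill form or a placebo") and include no weighing or impedance measurement. The list of dependent variables ends with "time to completion of the 5km TT, power output during the 5km TT, muscle oxygenation, plasma histamine levels".

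Section 2.0 expects that "blood and muscle microvascular oxygenation during heavy exercise will improve compared to placebo, ultimately improving exercise performance at altitude". The power paragraph of Section 8.0 adds "Using a one tailed test to match our directional hypothesis" and describes p < 0.05 as a "level (experiment-wise error rate"). That paragraph concerns arterial oxyhemoglobin saturation. No outcome is called primary.

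**The concern.** On the text, a cetirizine-placebo t-test of mass or percent fat has no data. The performance variables that need such a test, 5 km time and power, are assigned to none. Performance is half of the only aim, so a reader might think its analysis was left open.

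If either time or mean power could support the performance claim, and the tests could be one- or two-sided, the sponsor would have some freedom to choose after seeing results. The Bonferroni correction covers only pairwise comparisons within the 2 x 5 ANOVA, so it would not limit that freedom. At stake would be a performance conclusion with an error rate above 5%, and doubt about whether the reported test was the planned one.

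**Working it through.** **Which test fits which variable.** Each method in Section 8.0 implies a data layout:

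| Method | Values per subject | Variables that fit |
|---|---|---|
| Paired t | 1 per condition | 5 km completion time; any whole-trial summary |
| 2 x 2 ANOVA | pre and post, per condition | plasma histamine |
| 2 x 5 ANOVA | 5 per condition, one per km | ventilation, VO2, SpO2; other per-km measures |

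Completion time is a single number per trial, so only the first row fits. Power during the trial could be averaged (first row) or recorded per kilometre (third row), and the plan does not say which. Weight and percent fat, if measured only in Session 1, give one value per subject and no difference to test. The timeline figure is not available, so repeat measurement in Sessions 2 and 3 cannot be excluded. In either case no Aim 1 result depends on them.

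**The plan's own figure.** Section 8.0 gives about 9 subjects for d = 0.61, on saturation. With d read as the standardised paired difference, a one-sided paired t-test at 0.05 needs 19 for 80% power, so the 9 is not reproduced on that reading. That is a separate question. Here 9 and 15 serve only as possible numbers of completers. The plan gives no effect size or SD for time or power, so power for performance cannot be computed.

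**Error rate if two paired t-tests were run.** Assumptions: mean power is tested as well as time; the within-subject differences are bivariate normal, each scored so that positive means benefit; their correlation r is 0.90-0.99 (not from the documents). With no true effect, 300,000 simulated trials per setting give this probability that at least one test is significant:

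| Completers | Sides | r = 0.90 | r = 0.95 | r = 0.99 |
|---|---|---|---|---|
| 9 | one | 6.9% | 6.4% | 5.7% |
| 9 | two | 7.3% | 6.7% | 5.7% |
| 15 | one | 6.8% | 6.4% | 5.6% |
| 15 | two | 7.1% | 6.6% | 5.7% |

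Time alone gives 4.9-5.1%. The excess over 5% runs from 5.6 - 5.0 = 0.6 to 7.3 - 5.0 = 2.3 percentage points.

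**Disagreement between the two.** If the true standardised paired difference (dz) were 0.61 on both measures, borrowing the plan's d as an illustration, the one-sided verdicts with 9 completers would differ in 15.6%, 10.9% and 4.9% of trials at r = 0.90, 0.95 and 0.99.

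**Sidedness.** The observed dz needed for significance is the critical t divided by the square root of n:

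- n = 9: 1.860/3 = 0.620 one-sided; 2.306/3 = 0.769 two-sided.
- n = 15: 1.761/3.873 = 0.455 one-sided; 2.145/3.873 = 0.554 two-sided.

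The verdict turns on sidedness only between these limits. The hypothesis in Section 2.0 is directional and includes performance, so one-sided is the likelier reading. A reported t statistic with its degrees of freedom lets a reader obtain either p-value.

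**The case for a change.** The strongest case for a change is that illustrative wording does not settle the selection. Mean power fits the paired t-test as well as time does, nothing ranks the two, and the examples meant to guide the reader are variables with no pair in the text. The verdicts could differ in up to 15.6% of trials in the illustration above, and naming one endpoint would cost only a sentence.

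Part of this stands. Section 8.0 uses poor examples, does not name a test for completion time, and calls no outcome primary. The rest is weaker:

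- The mean-power test is supposed, not planned. Power is listed in the same way as dyspnea and perceived exertion, which Section 5.0 collects each kilometre. It could equally enter the 2 x 5 ANOVA, and then the two-test calculation does not arise in that form.
- Section 5.0 gives time a practical priority: subjects are told to cover the distance as fast as they can. This is not a formal ranking, but it makes time the natural measure of performance.
- The one-tailed statement and the experiment-wise rate stand in the same sentence. If that sentence governs performance, sidedness is settled. If it governs saturation only, no experiment-wise promise was made about performance. The two complaints cannot both hold.
- Naming 5 km time as the single performance endpoint would still leave saturation and performance unranked against each other. It would also pass over the repeated sprint trials, which Section 2.0 mentions and the procedures in Section 5.0 do not describe.

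**Conclusion.** No change to the plan follows. The observation about the text is accurate: the two examples are Session 1 screening measures, and 5 km time is not named. An analyst would nevertheless compare completion time between conditions with a paired t-test, because no other listed method fits, and would treat mass and percent fat as descriptors unless they were measured again.

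The error-rate argument does not carry the point. Its size is 0.6-2.3 percentage points, and it depends on an unstated paired test of mean power and an assumed correlation of 0.90-0.99. The 4.9-15.6% disagreement also borrows an effect size derived from arterial PO2. Clearer examples and a stated sidedness would make Section 8.0 easier to read, but would not alter what is measured or the evident test of 5 km time. This conclusion assumes that completion time is reported as one value per condition and that any power result is shown alongside it, not in its place.

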Upon arrival at the laboratory for Sessions 2 and 3, subjects will be asked to ingest a pill containing 10mg of Cetirizine or a gelatin placebo. Black colored (e.g. non-opaque) size 1 gelatin capsules will be purchased commercially. For placebo, the capsules will be filled with 10 mg of sugar-free gelatin, purchased from a local grocery store. Cetirizine will be purchased over-the-counter, and the 10mg pill will be encapsulated within the same black colored size 1 gelatin capsule as the placebo. The treatment will be double-blinded and the order will be randomized and counter-balanced. Pharmacokinetics of Cetirizine indicate peak plasma levels are achieved within 60 min, and as subjects will be at least 3 hours post-prandial, will not be delayed by recent diet.

Maximal oxygen uptake: The subject will be asked to warm up on the cycle ergometer for 10 minutes at a comfortable, self-selected pace. Subjects will be fitted with a) an oronasal face mask which covers the nose and mouth, b) a chest strap heart rate monitor, and c) a pulse oximeter sensor will also be placed on the subject's forehead to non-invasively measure arterial oxygen content. The subject will then be asked to pedal at a cadence between 80 and 110 rpm at a workload of 50W. The workload will be increased by 25W every minute until volitional exhaustion or until RPMs fall below 70 for 3 seconds. Expired air from the face mask is collected in a tube for the determination of oxygen content, CO₂ content, and expired ventilatory volumes.

Constant-load cycling: In sessions #2 and #3, subjects will be asked to complete five minutes of cycling at submaximal workloads equal to 60% and 75% of VO₂max, as determined in session #1. Subjects will have five minutes of passive rest after each 5-minute exercise bout.

5km cycle performance trial: Subject will be asked to complete 5km on the cycle ergometer in as short a time as possible (fit individuals typically take between 8 and 12 minutes). Subjects will be free to shift gears on the cycle and pedal at any cadence desired. Subjects will be given visual feedback on distance travelled and verbal feedback every 1km.

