Hypoxic inspirate: Altitude will be simulated by breathing a hypoxic inspirate. A commercially available, portable nitrogen generator (Colorado Altitude Training Systems) will be used to generate nitrogen rich air, in order to decrease the O₂ content to the specified level. The nitrogen generator will be set to produce an outflow of 14.3% O₂, equivalent to an altitude of 3000m / 9900 ft. Note that the mechanical design limits of the nitrogen generator only allows for a minimal O₂ level of 14.3%. Additionally, our laboratory O₂ analyzer will constantly monitor and record inspired oxygen levels. Hypoxic gas from the generator will be collected in two large meteorological balloons, to serve as the inspired air reservoir.

Blood sampling: In each of Sessions 2 and 3, subjects will be asked to give two blood samples of ~ 2-5 ml each: one prior to beginning cycle exercise, and one after completing the 5km time trial. Blood will be taken via routine venipuncture procedure from an antecubital vein using a 22g or smaller needle and a sodium EDTA treated (lavender top) vacutainer. Standard precautions will be used, and an experienced investigator will perform the venipuncture. Subjects will be free to choose the arm used for each venipuncture.

6.0 Reporting of Adverse Events or Unanticipated Problems involving Risk to Participants or Others

The primary investigator will report the frequency of monitoring and dates, summary of adverse events, assessment of external factors that impact safety of subjects, summary of subject privacy and research data confidentiality, and changes to the risk-benefit ratio. Adverse events include death, an injury requiring hospitalization, loss of information containing identifiable records, an unanticipated experience associated with intensive exercise, and other related events. Our intention is that the data from this study may be used in characterizing the athletic population, and may be used in longitudinal comparisons.

In the event of an adverse event, the PI will report immediately to and cooperate with the IRB in any necessary investigation. After two adverse events, the protocol will be evaluated for possible modification.

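### The pre- to post-exercise rise in plasma histamine cannot be separated from haemoconcentration, because posture is not fixed and no plasma-volume measure is planned

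*Combined protocol and SAP*

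**What the plan says.** Section 5.0 lists histamine among the dependent variables as a plasma level: "power output during the 5km TT, muscle oxygenation, plasma histamine levels". For Sessions 2 and 3 the same section describes the pre-exercise sample thus: "Subjects will be allowed to sit comfortably or lie down for 60 minutes. Following this rest period, approximately 5 ml of blood will be drawn". The blood-sampling paragraph confirms two samples per session, "one prior to beginning cycle exercise, and one after completing the 5km time trial".

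Between the two samples come a 10-minute warm-up, then "five minutes of cycling at submaximal workloads equal to 60% and 75% of VO₂max", then the time trial, in which "subjects will be asked to ride 5km, completing the distance in as short of a time as possible". On the second sample: "Immediately following the TT, approximately 5 ml of blood will be drawn from an antecubital vein".

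Section 8.0 assigns histamine to a 2 x 2 repeated measures ANOVA that "will be used to determine pre- vs. post-test differences across conditions with select dependent variables (e.g. plasma histamine").

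No section plans haematocrit, haemoglobin, plasma protein or any other index of plasma volume. None states a correction for haemoconcentration, and none fixes posture before or during either draw. The documents do not say outright that histamine will be analysed uncorrected. That reading follows from the absence of any correction.

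**The concern.** A concentration is an amount divided by a volume. The plan treats a pre-to-post difference in concentration as if only the amount could change, but the procedures around the two draws can also change the volume. Two influences push the same way: water leaves plasma during heavy exercise, and a subject who was lying before the first draw has a more dilute starting sample than one who was sitting. Both make the second value higher relative to the first without any histamine being released.

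At stake is one mechanistic statement. Section 1.0 argues that heavy exercise releases histamine in the airways and that this slows oxygen diffusion. Plasma histamine is the only listed dependent variable that could show such release in these subjects, and the time effect is the test of it. A significant rise would naturally be reported as release. Because the error is a bias and not noise, testing 15 subjects instead of 9 makes a spurious rise more likely to reach significance, not less.

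**Working it through.** **Inputs from the documents.** Two draws in each of two sessions, one before any cycling and one immediately after the TT; free choice of sitting or lying for 60 minutes; a 2 x 2 ANOVA; about 9 subjects needed and 15 to be tested (Sections 5.0 and 8.0). The plan gives no figure for histamine (level, expected change, SD or assay variation) or for plasma volume, so there is nothing of its own to reproduce.

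**Assumptions.** Fraction of plasma volume lost between draws, L = 5 to 20%. Within-subject CV of histamine = 10 to 30%. Posture shift of up to 10%.

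**Step 1: apparent rise with no release.** If all histamine stays in plasma, post/pre = 1/(1 - L), so the apparent rise is 1/(1 - L) - 1. If instead the departing water carries histamine at a fraction s of the starting plasma concentration, post/pre is about (1 - sL)/(1 - L).

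| L | s = 0 (fully retained) | s = 0.5 | s = 1 (leaves freely) |
|---|---|---|---|
| 5% | 5.3% | 2.6% | 0% |
| 10% | 11.1% | 5.6% | 0% |
| 15% | 17.6% | 8.8% | 0% |
| 20% | 25.0% | 12.5% | 0% |

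For example, with L = 10%, 1/0.90 - 1 = 11.1% and 0.95/0.90 - 1 = 5.6%. The s = 0 column is the upper bound.

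**Step 2: effect on the time test.** The 2 x 2 design was simulated with no release, full retention, loss with an SD of 3 percentage points and the same mean in both conditions, a two-sided 0.05 level and 20,000 runs. Rejection rates of the time effect (n = 9 / n = 15):

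| Mean L | CV 10% | CV 20% | CV 30% |
|---|---|---|---|
| 5% | 0.25 / 0.43 | 0.10 / 0.14 | 0.07 / 0.09 |
| 10% | 0.74 / 0.95 | 0.26 / 0.44 | 0.14 / 0.22 |
| 15% | 0.98 / 1.00 | 0.53 / 0.79 | 0.27 / 0.45 |

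These rates are also upper bounds, because they assume full retention.

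**Step 3: effect on the condition-by-time test.** In the same runs its rejection rate was 0.044 to 0.049, which is nominal. A stress case assumed a 7.5% posture shift, with 20% of subjects lying down on placebo and 60% on cetirizine. With L = 10% the interaction rejected no more than 0.08 of the time.

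**Step 4: noise from free posture.** If posture is chosen at random each session and the shift is 10%, the pre value gains an SD of 0.5 x 10% = 5%. The interaction contrast uses four values, two of them pre values, so its variance goes from 4CV² to 4CV² + 2(0.05)².

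- CV 10%: sqrt(0.045/0.040) = 1.06, an SD about 6% larger.
- CV 20%: sqrt(0.165/0.160) = 1.016, about 1.6% larger.

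**The case against.** The strongest reply is that the trial is about cetirizine against placebo, and that comparison is protected. Sessions are randomised, counterbalanced and double-blinded, with the same rest, bouts, TT and draws, so water loss common to both sessions largely cancels. This stands, and Step 3 supports it. A reader might infer that the treatment contrast on histamine is biased. The documents do not support that: it would need posture or effort to differ systematically between conditions, and even the marked imbalance tried above moved the error rate only slightly.

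Second, Specific Aim 1 concerns performance and arterial oxygenation. Histamine is in neither the aim nor the stated expectation, and Section 1.0 takes exercise-induced release from cited literature. This also stands and limits the importance of the point, but the plan still collects the samples and tests the time effect.

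Third, histamine is a small molecule and may leave plasma with the water. The full-retention figures are then too high, and multiplying the post value by (1 - L) would over-correct. This stands. It is a reason not to replace the measured values with corrected ones, but it does not show that the artefact is absent.

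Fourth, every magnitude is assumed. That is correct. If true release is large compared with the artefact, haemoconcentration inflates the rise but does not create it.

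**Conclusion.** The point holds for the time effect only. As planned, a significant pre-to-post rise in plasma histamine cannot be attributed to release, because a water shift in the same direction is neither controlled nor measured. On an assumed plasma-volume loss of 5 to 20%, the spurious rise is at most 5.3 to 25.0%, and it falls towards zero if histamine leaves freely with the water. Whether this would produce a significant result depends on assay and biological variation that the documents do not give. At 10% loss and full retention, the false-positive rate ranges from 0.14 (CV 30%, n = 9) to 0.95 (CV 10%, n = 15).

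A reader might also infer that free posture seriously weakens the condition-by-time test in so small a trial. Step 4 does not bear that out: the SD rises by about 6% at most across the CVs considered. TT time, SpO2 and the sample-size calculation do not depend on plasma histamine. This is a low-cost improvement to a mechanistic outcome, not a threat to the main comparison. Its one urgency is that whole-blood haematocrit cannot be recovered once plasma has been separated.

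**What to change.** - **Section 5.0, posture.** Require the same seated posture for at least the last 30 minutes before the pre-exercise draw in both sessions, and the same posture at the post-exercise draw in both sessions.
- **Section 5.0, blood.** Read haematocrit (Hct), and haemoglobin (Hb) if available, from each EDTA tube before plasma is separated. With a constant amount of haemoglobin, retained plasma volume is 1 - L = (Hb pre / Hb post) x (1 - Hct post)/(1 - Hct pre). With haematocrit alone and constant red-cell volume, replace the first ratio by Hct pre / Hct post.
- **Section 8.0.** Keep the 2 x 2 ANOVA on measured histamine. Add the same ANOVA with post-exercise values multiplied by (1 - L) as a sensitivity analysis. State that a rise will be attributed to histamine release only if it holds in both.

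**Cost.** A few sentences of text and four haematocrits per subject (2 draws x 2 sessions), or 60 readings for 15 subjects, with no extra venipuncture. The downsides are a few minutes of bench work and the chance that full correction over-corrects a small solute, which is why both results are shown.
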